## 5. Introduction

### 5.1. Background

Continuous ECG monitoring (telemetry) is indicated and highly valuable for monitoring patients at risk for cardiac events. The use of telemetry has gradually expanded to lower-risk patients for whom such monitoring may not provide substantial clinical benefit. Moreover, clinicians often use telemetry with the intent to provide enhanced vigilance over patients' clinical status, even when that patient does not have a

This document is electronically controlled. Printed copies are considered uncontrolled.

**Confidential**

Protocol #: COVMOPO0561

Rev E 09AUG2017

significant underlying cardiac risk (1,2). The American Heart Association (AHA) has published a guideline indicating that low-risk patients do not require telemetry, as outcomes of these patients are not affected by telemetry monitoring (3,4). Despite these recommendations and evidence, one study reported that three of the top diagnoses of patients admitted to telemetry units are not clinically indicated, per AHA guidelines (4) and other studies report non-indicated monitoring may account for ~35% of patient telemetry days (5,6).

Telemetry in non-indicated patients has been shown to have limited clinical benefit. In lower-risk patients, clinically significant telemetry-monitored events are rare. The use of telemetry in these patients does not often change clinical management. In a retrospective analysis of 501 patients on telemetry, Benjamin and colleagues reported the incidence of arrhythmias on non-indicated days to be low (3.1 per 100 non-indicated days) as compared to indicated days (20.7 per 100 indicated days) (5). Dressler et al redesigned their cardiac telemetry sets and reduced telemetry use by 70% with no change in code blue, mortality, or rapid response team activation rates (7).

Overuse of telemetry in lower-risk patients can overburden the hospital system and was highlighted by the Choosing Wisely campaign as one of five "opportunities for improved healthcare value (8)." As such, the authors stated that telemetry overuse "can be linked to increased length of stay, boarding in the emergency department, reduced hospital throughput, increased ambulance diversion, increased operation costs," and "lead to a false sense of security and alarm fatigue (8)." In addition to the direct costs of telemetry, there are indirect costs related to Emergency Department (ED) backlog and hospital overcrowding. One study estimated that a delay in the ED of more than three hours before admission to a telemetry bed results in an opportunity cost in lost revenue of about \$204 per patient (9). Other studies estimate savings ranging from \$250,000 – \$4.8 million annually through adherence to the AHA recommendations for telemetry use (5,7).

Overall, available data indicate that reducing the incidence of unnecessary telemetry could increase bed availability, shorten length of stay, and decrease the cost of care with relatively low clinical risk. Recent advances in monitoring technology may allow for cost-effective monitoring alternatives of key vital signs, provide for the early detection of patients who warrant increased attention, aid in ED triage, and improve overall caregiver workflow. These newer technologies have the ability to monitor multiple variables at once, including single-lead ECG and respiratory rate, and thus allow for the pre-programming of 'smart-alerts' better designed to detect clinically significant changes in patient condition. In these patients where physiologic monitoring is desired yet clinical diagnoses do not meet the AHA criteria for cardiac telemetry, such alternative surveillance monitoring strategies may provide acceptable clinical benefit while reducing hospital burden. This may be enabled through the provision of monitoring and enhanced vigilance within the general medical/surgical floor without requiring patient transfer to a dedicated telemetry bed.

While these newer monitoring technologies are novel, prospective evidence to support surveillance monitoring is limited. This study is designed to address the gap in evidence to compare surveillance monitoring to telemetry monitoring.

## 5.2. Purpose

The purpose of the study is to evaluate the impact of surveillance monitoring versus telemetry monitoring on clinical, healthcare economics, resource utilization, and qualitative outcomes.

This document is electronically controlled. Printed copies are considered uncontrolled.

## 6. Objectives and Endpoints

### 6.1. Objectives

#### 6.1.1. Primary Objective

The primary objective of this study is to compare hospital length of stay (LOS) between the surveillance monitoring and telemetry monitoring period on patients without AHA telemetry indication.

#### 6.1.2. Secondary Healthcare Economic and Resource Utilization Objectives

1. Compare telemetry bed, emergency department (ED) bed, and intensive care unit (ICU) bed availability between monitoring periods
2. Compare associated health care costs between monitoring periods
3. Compare the number of ICU, ED, PACU, and telemetry delays in transfer between monitoring periods
4. Compare the number of hospital unit transfers between monitoring groups
5. Compare the number of unplanned ICU transfers between monitoring groups
6. Compare ICU LOS for subjects having unplanned transfers to the ICU between monitoring groups
7. Compare the number of unnecessary diagnostic tests and therapeutic procedures generated by artifacts and/or misdiagnosis between monitoring groups

#### 6.1.3. Secondary Clinical and Qualitative Objectives

1. Compare the number of Rapid Response Team (RRT) interventions between monitoring groups
2. Compare survival rates post RRT interventions between monitoring groups
3. Compare code blue rates between monitoring groups
4. Compare unplanned intubations between monitoring groups
5. Compare time of RRT activation to time of threshold notifications from SM system following clinical deterioration events
6. Assess clinical team satisfaction with surveillance monitoring and study product
7. Assess patient satisfaction with surveillance monitoring and study product
8. Assess perceptions of clinicians who prescribe telemetry to patients without AHA indication
9. Assess clinicians' perceptions on telemetry utilization and impact on hospital resource utilization and patient flow

This document is electronically controlled. Printed copies are considered uncontrolled.

## 6.2. Endpoints

### 6.2.1. Definition of Primary Endpoint

1. Length of stay

**Definition:** The overall hospital LOS; time(in minutes) of admission to discharge during indexed hospitalization.

### 6.2.2. Definition of Secondary Healthcare Economic and Resource Utilization Endpoints

1. Telemetry bed, ED, and ICU bed availability

**Definition:** Daily available number of beds available in both telemetry ED, and the ICU measured daily in hours from 12:00 AM to 11:59 PM.

2. Associated health care costs

**Definition:** Costs attributable to the primary and secondary clinical and resource utilization endpoints.

3. ICU, ED, PACU, and telemetry delays in transfer

**Definition:** Number of patients delayed admission to the ICU, ED, PACU, and to a telemetry bed.

4. Hospital unit transfers

**Definition:** Number of inpatient transfers from one unit to another unit during course of hospital stay.

5. Unplanned ICU transfers

**Definition:** Direct transfers from either study monitoring group to the ICU where the transfer was not planned during the hospital stay. For example, a transfer may be planned in advance of certain procedures for high risk patient as a preventative measure. The study team will determine if transfer were considered planned versus unplanned by review of the medical record.

6. LOS for ICU transfers

**Definition:** The LOS (time in minutes) in the ICU for subjects who have an unplanned transfer to the ICU.

7. Diagnostic tests and therapeutic procedures generated by artifacts and/or misdiagnosis

**Definition:** Any diagnostic test or therapeutic procedure that was performed because of an ECG artifact or misdiagnosis made by clinician using monitoring technology

This document is electronically controlled. Printed copies are considered uncontrolled.

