### 8.1.2. Wearable Physiological Monitor

The BioModule™ BH3-M2 sensor is a wearable physiological monitoring device intended for monitoring adults in hospitals and alternate care settings. When combined with the BioModule Holder and snap ECG electrodes, it becomes the BioPatch™ wireless device. It continuously collects a patient's physiologic data including ECG, HR, RR, body orientation, and activity and transmits data to the Vital Sync™ VPMP every [REDACTED]. The BioModule™ sensor provides a [REDACTED], single-lead ECG that records either automatically or on demand when a patient's heart or respiration rate crosses clinician-assigned thresholds.

The BioModule™ sensor is a Class II device and 510(k) cleared by the FDA.

[figure not shown]
BioModule™

This document is electronically controlled. Printed copies are considered uncontrolled.

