### 10.1. Monitoring Group Assignment

#### Telemetry Monitoring (TM) Group, Control

The TM group will serve as the control group and will be monitored via the site's standard of care telemetry practice/protocol. Subjects will continue to be enrolled in the study if subjects are transferred to medical-surgical unit after initial period of TM. Subjects will be tracked daily to confirm continuing eligibility for the study. Temporary alternate monitoring modalities will be allowed per the discretion of the Investigator. If subject no longer meets eligibility criteria, the subject should be withdrawn and study completion date will be the date the subject became ineligible not the date the study team discovered the ineligibility.

If a subject is transferred to another hospital unit or telemetry is discontinued, subject will continue to be enrolled in the study.

If subject is transferred to ICU, there will be an exception to the requirement of tracking daily continuing eligibility. It is expected for additional care and monitoring to be administered during the ICU stay and AHA indication to change. Once subject is transferred from the ICU back to a lower acuity unit, eligibility criteria will be reassessed and documented. If subject no longer meets eligibility criteria upon return to

This document is electronically controlled. Printed copies are considered uncontrolled.

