### **Surveillance Monitoring (SM) Group**

Subjects in the SM group will alternatively be admitted to a medical surgical unit and placed with the study device following study enrollment. Hospital staff will utilize SM for the duration of study enrollment.

The sponsor and investigator will collaborate to implement the SM strategy. This implementation could include a variety of strategies based on the site's facilities, staffing resources, and IT infrastructure. The Vital Sync™ IM & VPMP conveys physiologic data, waveforms, and will provide visual alerts and annunciation alarms. Alert and alarm thresholds will be customized as needed to align with the hospital's protocols. Data from the remote monitoring platform will be accessed at a central workstation, a workstation on wheels, a bedside tablet, and/or smartphones/tablets.

Subjects will be tracked daily to confirm continuing eligibility for the study. Temporary alternate monitoring modalities will be allowed per the discretion of the Investigator. If subject no longer meets eligibility criteria, the subject should be withdrawn and study completion date will be the date the subject became ineligible not the date the study team discovered the ineligibility.

If a subject is transferred to another hospital unit, subject will continue to be enrolled in the study. However, the subject will be removed from SM during the transfer including placement of BioModule. When the subject transfers back to the medical-surgical unit, SM should resume as soon as reasonably possible per discretion of the Investigator until discharge from the hospital or end of study enrollment.

If subject is transferred to ICU, there will be an exception to the requirement of tracking daily continuing eligibility. It is expected for additional care and monitoring to be administered during the ICU stay and AHA indication to change. Once subject is transferred from the ICU back to a lower acuity unit, eligibility criteria will be reassessed and documented. If subject no longer meets eligibility criteria upon return to lower acuity unit, the subject should be withdrawn from the study. If subject meets eligibility criteria daily, subject will resume SM procedures and daily tracking of eligibility criteria.

[figure not shown]
This document is electronically controlled. Printed copies are considered uncontrolled.

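### Secondary endpoint 7 limits the artifact part of its count to ECG, although its objective says artifacts in general and surveillance monitoring also applies thresholds to respiration rate

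*Protocol*

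**What the plan says.** The objective in Protocol 6.1.2, item 7, is to "Compare the number of unnecessary diagnostic tests and therapeutic procedures generated by artifacts and/or misdiagnosis between monitoring groups". The matching endpoint in Protocol 6.2.2, item 7, is headed "Diagnostic tests and therapeutic procedures generated by artifacts and/or misdiagnosis". Neither limits the artifact to a particular signal.

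The operative definition under that heading has two limbs: "Any diagnostic test or therapeutic procedure that was performed because of an ECG artifact or misdiagnosis made by clinician using monitoring technology". SAP 4.2.2, item 7, repeats it. Nothing in either document explains why ECG is singled out.

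On the SM side, Protocol 8.1.2 lists ECG, heart rate, respiration rate, body orientation and activity among the data collected, and describes a single-lead ECG that "records either automatically or on demand when a patient's heart or respiration rate crosses clinician-assigned thresholds". Protocol 8.4 says clinicians are notified by alarms and audible alerts. Section 10.1 adds that "Alert and alarm thresholds will be customized as needed to align with the hospital's protocols". Section 10.2.1 has staff confirm that respiration rate is displayed on the central station.

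On the control side, Protocol 5.1 equates telemetry with ECG: "Continuous ECG monitoring (telemetry) is indicated and highly valuable for monitoring patients at risk for cardiac events". What the TM group actually receives is left to the hospital. Under Section 10.1, subjects "will be monitored via the site's standard of care telemetry practice/protocol".

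**The concern.** The endpoint is meant to compare how much unnecessary work each monitoring method generates. The artifact limb covers the one signal that the protocol attributes to telemetry, but only part of what SM measures and sets thresholds on. Suppose a spurious respiration-rate alarm leads to a test, the result is normal, and nobody has diagnosed anything wrongly. That test is unnecessary work caused by monitoring, yet on a literal reading neither limb counts it, and none of the other listed endpoints does.

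If such tests arise in the SM group and not in the TM group, the comparison tilts toward SM. The effect could extend to secondary endpoint 2, because health care costs are defined there as those attributable to the primary and secondary clinical and resource utilization endpoints.

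**Working it through.** The documents give no rate, effect size or power for this endpoint, so there is no planned figure to reproduce. The check is a reading of the definition, followed by an illustration of size.

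**Step 1: which events are counted on a literal reading.**

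| Prompt for the test | Misdiagnosis made? | Counted? |
|---|---|---|
| ECG artifact | no | yes, first limb |
| ECG artifact | yes | yes, either limb |
| Spurious respiration-rate alarm | yes | yes, second limb |
| Spurious respiration-rate alarm | no | no, unless misdiagnosis is read broadly |

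The last row is the gap. The objective would include it, because it refers to artifacts of any kind.

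**Step 2: whether the second limb closes the gap.** Misdiagnosis is not defined. If it were read broadly enough to take in every test ordered on a false signal, the separate mention of ECG artifact would be largely redundant. Naming it separately suggests that artifact without misdiagnosis counts for ECG and not for other signals. No attribution rule is given for item 7. Item 5 in the same section does assign its planned-or-unplanned decision to the study team, by medical-record review.

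**Step 3: size, under assumptions.** Let

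- r = share of SM false-signal work-ups that come from respiration rate (assumed 10%, 25%, 50%);
- m = share of those that the misdiagnosis limb captures (assumed 0, one half, all);
- true work-up rates equal in the two groups, and every TM work-up counted.

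Then the counted SM/TM ratio is 1 − r(1 − m). For example, r = 0.25 and m = 0.5 give 1 − 0.25 × 0.5 = 0.875.

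| r | m = 0 | m = 0.5 | m = 1 |
|---|---|---|---|
| 10% | 0.90 | 0.95 | 1.00 |
| 25% | 0.75 | 0.875 | 1.00 |
| 50% | 0.50 | 0.75 | 1.00 |

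**Step 4: if telemetry also alarms on respiration rate.** With a share t of TM work-ups from that source and the same m, the ratio becomes [1 − r(1 − m)] / [1 − t(1 − m)]. When t = r it is 1.00 for any m below 1. With r = 0.25, t = 0.10 and m = 0 it is 0.75 / 0.90 = 0.83. If t exceeds r, the omission favours TM. The direction therefore depends on a fact that the documents do not state.

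**The case against.** A reader might infer that the endpoint counts nothing but tests caused by ECG artifact, that false respiration-rate alarms are peculiar to SM, and that SM therefore looks better by definition. The case against that reading is strong, and most of it stands.

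- The definition has a second limb that is not limited to ECG or to either system. A clinician who reaches a wrong diagnosis from a false respiration rate, and acts on it, is counted. Even without a clear diagnosis, a broad reading of the undefined term could bring the test in.
- The parameters of the site's telemetry are not described. The sentence in Protocol 5.1 is general background, and the TM group follows local practice. The exclusion of patients prescribed other continuous monitoring, such as capnography or pulse oximetry, does not settle whether the telemetry equipment itself alarms on respiration rate.
- The protocol does not say how the sensor derives respiration rate. It is worn with ECG electrodes, and the text after its description is redacted. Some spurious respiration-rate values might share a cause with an ECG artifact and be counted under the first limb.
- The threshold sentence in Protocol 8.1.2 concerns triggering of the ECG recording. That SM raises alarms comes from Sections 8.4 and 10.1, so a respiration-rate alarm is an inference from these passages together, though a natural one.
- Item 7 is one of 16 secondary endpoints (7 economic and resource, 9 clinical and qualitative) in a single-center pilot, and it has no power calculation of its own.

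These points limit the claim about direction and size. They do not remove the mismatch: the written rule is narrower than the objective it serves, and closing the gap depends on a reading of misdiagnosis that the text does not secure.

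**Conclusion.** The concern holds as a definition narrower than its objective. In both documents the artifact limb of endpoint 7 should extend to every monitored signal. As written, tests prompted by a spurious respiration-rate alarm without misdiagnosis go uncounted unless the second limb is read broadly.

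A bias in favour of SM is conditional. It requires that the site's telemetry has no respiration-rate alarm, or fewer work-ups from one than SM, and that the misdiagnosis limb does not capture these tests in full. Under the assumptions in the working, with no such alarm in TM, the counted ratio runs from 0.90 to 0.50 with no capture and is 1.00 with full capture. The 10% to 50% range is an assumption, not an estimate, and a share near zero is equally compatible with the documents. The effect on the cost endpoint is possible but of unknown size. Nothing here touches the primary length-of-stay comparison.

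**What to change.** In Protocol 6.2.2, item 7, and SAP 4.2.2, item 7, replace the words that confine the first limb to ECG artifact with: *an artifact in any signal or alarm of the monitoring system in use (ECG, heart rate, respiration rate or other monitored parameter)*. State that the definition applies identically to both groups.

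Add one sentence on attribution, following item 5: the study team decides from the medical record, by the same rule in both groups, whether a test or procedure was prompted by an artifact or a misdiagnosis.

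The cost is one phrase and one sentence in each document, plus record review for the tests concerned. The downside for the sponsor is that the SM count may rise. A table of total tests per subject from billing records would not be a substitute: totals include necessary tests, and a comparison between consecutive, non-randomized phases is open to differences in case mix and period.

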### 6.2.3. Definition of Clinical and Qualitative Endpoints

1. RRT interventions

**Definition:** RRT's that are activated due to clinical deterioration as reported by the hospital or subject's medical record.

2. Survival rates post RRT interventions

**Definition:** Survival at discharge or study completion following RRT activation.

3. Code blue rates

**Definition:** Code blue teams that are initiated due to cardiopulmonary arrest as reported by the hospital or subject's medical record.

4. Unplanned intubations

**Definition:** An intubation and mechanical ventilation that was not planned during the course of the hospital stay.

5. Time of RRT activation to time of a threshold notification(s) from the SM system following clinical deterioration events

**Definition:** Time of RRT activation is the time that a clinician called or initiated the RRT team. Time of a threshold notification(s) is the time when the SM system alerts or alarms when a hospital protocol-defined threshold is exceeded.

6. Clinical team satisfaction with surveillance monitoring and study product

**Definition:** Clinical team (nurse or physician) who treated at least one study subject will be asked to take a qualitative survey on satisfaction and confidence.

7. Patient satisfaction with surveillance monitoring and study product

**Definition:** Each subject will be asked to take a qualitative survey on satisfaction and comfort and the end of enrollment.

8. Perceptions of clinicians who prescribe telemetry to patients without AHA indication

**Definition:** Each eligible clinician will be asked to take a qualitative survey focused on the AHA guidelines and the monitoring modalities of the study.

9. Clinicians' perceptions on telemetry utilization and impact on hospital resource utilization and patient flow

This document is electronically controlled. Printed copies are considered uncontrolled.

**Definition:** Each eligible clinician will be asked to take a qualitative survey focused on telemetry utilization and the monitoring modalities of the study.

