## 11.2. Potential Benefits

Subjects' participation in this study may offer no additional benefit in respect to the same monitoring provided outside of the study.

Possible benefits for participating in this study include the following (although others are possible):

- Subjects in SM arm may benefit from the alternative surveillance monitoring strategy via detection of clinical deterioration during the course of hospital stay.

There is, however, the potential for benefiting future patients should this study lead to the development of safer, more accurate, more cost-effective, and easier-to-use medical monitoring devices.

Since this is not a treatment study, the alternative is to not participate in the study.

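### Survival after RRT and ICU length of stay are compared only among subjects selected by a post-assignment event, so either group can look better or worse with identical deaths or ICU time

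*Protocol*

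**What the plan says.** Two secondary endpoints are defined only for subjects who had a particular event in hospital:

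- Protocol 6.2.3, item 2: "Survival at discharge or study completion following RRT activation".
- Protocol 6.2.2, item 6: "The LOS (time in minutes) in the ICU for subjects who have an unplanned transfer to the ICU".

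SAP 4.2.3 and 4.2.2 carry the same definitions. The objectives make both of them between-group comparisons: "Compare survival rates post RRT interventions between monitoring groups" (Protocol 6.1.3) and "Compare ICU LOS for subjects having unplanned transfers to the ICU between monitoring groups" (Protocol 6.1.2).

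The two selecting events are themselves compared as outcomes: "Compare the number of Rapid Response Team (RRT) interventions between monitoring groups" and "Compare the number of unplanned ICU transfers between monitoring groups".

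The Protocol links the new monitoring to these events. The background (5.1) says that newer monitoring may "provide for the early detection of patients who warrant increased attention". Section 8.4 has the system notify clinicians of clinical distress. Section 11.2 says: "Subjects in SM arm may benefit from the alternative surveillance monitoring strategy via detection of clinical deterioration during the course of hospital stay". None of these places states whether RRT calls or ICU transfers should rise or fall relative to telemetry.

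SAP 7.9 lists both endpoints without a method of their own, so the general two-sided 0.05 tests of SAP 7.2 apply. Neither document defines a mortality endpoint over all subjects, or ICU time per subject over all subjects.

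**The concern.** The denominator of each comparison is formed after assignment, by an event that the monitoring method could influence. If one method triggers more RRT calls in subjects who would have survived anyway, its survival percentage after RRT rises although no death is prevented. If it leads to more short ICU stays, its mean ICU stay falls although no ICU time is saved. Fewer calls or fewer short stays do the reverse, so a real saving in ICU use can appear as a longer stay.

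The two results would naturally be read as a safety finding and an efficiency finding. The plan has no all-subject counterpart to set beside them, so a reader has no named comparison that shows whether deaths or ICU use differed.

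**Working it through.** **Inputs.** The documents give no rate for RRT calls, unplanned ICU transfers or deaths, and no power for these endpoints. All event counts below are assumed. The only document figures used are group sizes: 132 per group (Protocol 13.1, SAP 6) and the recruitment ceiling of 220 per group (Protocol 13.1; SAP 5 and 6 give 140).

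**The plan's own figure.** The 132 concerns hospital LOS and does reproduce. On the log scale SD = √ln(1 + 0.65²) = 0.594 and the margin is ln 1.2 = 0.182. Then n = 2 × (1.645 + 0.842)² × 0.594² / 0.182², which at full precision rounds up to 132 for one-sided 0.05 and 80% power. It has no bearing on the present point beyond supplying a denominator.

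**Survival after RRT.** With r RRT subjects and d deaths, all assumed to follow an RRT, conditional survival is 1 − d/r. All-subject mortality is d/N.

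| Deaths in each group | RRT subjects TM / SM | Survival after RRT TM / SM | Mortality in both groups, N = 132 (N = 220) |
|---|---|---|---|
| 2 | 8 / 16 | 75.0% / 87.5% | 1.5% (0.9%) |
| 2 | 16 / 8 | 87.5% / 75.0% | 1.5% (0.9%) |
| 4 | 8 / 16 | 50.0% / 75.0% | 3.0% (1.8%) |
| 4 | 16 / 8 | 75.0% / 50.0% | 3.0% (1.8%) |

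More generally, let f be TM fatality after RRT and k the ratio of SM to TM RRT subjects, with equal group sizes and equal deaths. SM survival is then 1 − f/k.

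| f | TM survival | SM, k = 0.8 | SM, k = 1.25 | SM, k = 1.5 | SM, k = 2.0 |
|---|---|---|---|---|---|
| 0.10 | 90% | 87.5% | 92.0% | 93.3% | 95.0% |
| 0.20 | 80% | 75.0% | 84.0% | 86.7% | 90.0% |
| 0.30 | 70% | 62.5% | 76.0% | 80.0% | 85.0% |

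With deaths equal, the sign of the apparent difference depends only on whether k is above or below 1.

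**ICU length of stay.** The conditional mean is total ICU minutes divided by the number of transferred subjects. The all-subject mean divides the same total by N. One day is 1,440 minutes.

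| Scenario | Transferred | ICU days | Mean if transferred (min) | Per subject, N = 132 (min) |
|---|---|---|---|---|
| TM: five 1-day and five 5-day stays | 10 | 30 | 4,320 | 327 |
| SM: same total, more transfers | 15 | 30 | 2,880 | 327 |
| SM: five extra 1-day stays | 15 | 35 | 3,360 | 382 |
| SM: five 1-day stays averted | 5 | 25 | 7,200 | 273 |

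In the third row SM uses more ICU time and looks better on the conditional mean. In the fourth it uses less and looks worse. At N = 220 the last column reads 196, 196, 229 and 164 minutes.

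**Precision.** At assumed RRT rates of 3% to 10%, a group would have about 4 to 13 RRT subjects (N = 132) or 7 to 22 (N = 220). Fisher's exact test gives p = 0.58 for 6/8 against 14/16 and p = 0.36 for 4/8 against 12/16. Differences of this size would not reach significance; the risk lies in how the percentages are read.

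**The case against.** Several counter-arguments have weight.

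- **Deaths are captured elsewhere.** All SAEs are collected, death is an SAE criterion (Protocol 12 and 12.2), and the safety analysis covers all participants, with group differences and 95% confidence intervals (SAP 7.1.3, 7.2). A reader might infer that mortality goes unrecorded; the documents do not support that. The mitigation is partial. Death is not a named comparison, and AE recording starts at attachment of the study devices and stops at withdrawal (Protocol 12, SAP 7.10). TM subjects have no BioModule placed (Protocol Table 1), so their start point is unclear.
- **Other endpoints are not event-selected.** RRT interventions, code blues, unplanned intubations, unplanned ICU transfers and hospital LOS are compared in the whole groups. These show that the denominators differ, but do not supply a comparison of deaths or ICU time.
- **A reader could rebuild the totals.** SAP 7.2 reports counts and means, so ICU minutes can be recovered as n × mean, and deaths after RRT from the frequencies. This holds, but it misses deaths without an RRT and gives no interval or test.
- **A reader might infer that SM is intended to trigger earlier or more frequent RRT calls than telemetry, and hence that the bias favours SM.** The documents do not support this. The comparator is continuous telemetry, the primary aim is non-inferiority, and the text on detection claims no advantage in timing over telemetry and no expected direction. Only the possibility of an effect is established.
- **Consequence is limited.** These are two of 16 secondary objectives (7 + 9), without multiplicity control (SAP 7.5), in an unblinded, non-randomised, single-centre pilot. The selection adds to confounding by phase; there is no randomised comparison for it to break. This argues for low weight, but does not justify keeping an avoidable source of bias.

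**Conclusion.** The point holds as a minor one. Both comparisons condition on a post-assignment event that the plan itself treats as an outcome, and the arithmetic shows that either group can look better or worse with identical deaths or identical total ICU time. No direction of bias is established.

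The sizes (75% against 87.5% survival; 4,320 against 2,880 minutes) are illustrations. They rest on assumed counts, equal group sizes and, for survival, every death following an RRT. With realistic numbers the comparisons would also be very imprecise.

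Two features of the plan add selection in the same subjects. Study staff judge which transfers are unplanned (Protocol 6.2.2) without blinding (10.5). Subjects who are ineligible on return from the ICU are withdrawn (10.1), which can bring forward the study-completion time at which survival may be assessed.

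**What to change.** In SAP 4.2 and 7.9, with matching wording in Protocol 6.2.2 and 6.2.3, make the two between-group comparisons over all subjects in the analysis set:

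1. In-hospital death by discharge or the end of the 30-day period, per subject. State when the 30 days start, since Protocol 7.1 counts from enrollment and 10.2.3 from admission.
2. Unplanned-ICU minutes per subject, set to zero where there was no unplanned transfer, with a rank or bootstrap comparison.

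Include withdrawn subjects, using the final outcomes data that Protocol 10.10 and SAP 7.4 take from the medical record, and report how many in each group are incomplete. Keep survival after RRT and ICU stay among transferred subjects as descriptive summaries, shown beside the event counts and without p-values.

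The cost is small wording changes in both documents; changing the SAP alone would leave it at odds with the Protocol definitions. No new visits are needed. The downsides are many zeros in the ICU measure and possibly missing later deaths or ICU minutes in subjects withdrawn after an ICU stay. The all-subject comparison does not remove that second problem, which is why the incomplete cases should be counted.
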